10.2.2 Stopping Criteria

10.2.2.1 General Stopping Criteria

The study will be discontinued if any unacceptable safety findings are identified. This decision will be made jointly by the Principal Investigator (or deputy) and the Sponsor. A written

¹ With the 12:6 ratio of active to placebo, if all 6 participants randomised to placebo are in the first 14 participants who are dosed, this will ensure the minimum of 8 participants will have received active vaccine.

document signed by the Principal Investigator (or deputy) and Sponsor will be produced ratifying the decision.

Individual participants may also be withdrawn for any of the reasons outlined in [Section 10.5.5](#).

10.2.2.2 Dose Escalation Stopping Criteria

Dose escalation will be temporarily stopped pending evaluation of all available data if any of the following criteria are fulfilled:

- If one of the sentinel group or more than 20% of the participants in a cohort experience a severe systemic reaction (including anaphylactoid reactions) related to the ZH9PA/ZH9 vaccine (study agent).
- If one of the sentinel group or more than 20% of the participants in a cohort experience a persistent febrile reaction ($>38.5^{\circ}\text{C}$ for ≥ 12 hours) related to the study agent.
- If one or more participants experience a serious adverse event (SAE) related to the study agent.
- If two or more participants in the same cohort, experience 'severe' non-serious adverse reactions (i.e. severe non-serious adverse events, independent of system-organ-class, considered at least possibly related, to the study agent).

Individual participants may also be withdrawn for any of the reasons outlined in [Section 10.5.5](#).

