6 ETHICS

6.1 Research Ethics Committee or Institutional Review Board

This study protocol will be submitted to the Research Ethics Committee (REC) for review to confirm provision of a favourable opinion. The favourable opinion of the REC must be obtained before commencement of any study procedures.

The favourable opinion is conditional upon the Sponsor registering the clinical trial in a publicly accessible database, within 6 weeks of the first participant recruited.

All substantial protocol amendments must receive favourable opinion from the REC responsible for the study. Non-substantial amendments will not require favourable opinion from the REC.

If the study is stopped due to adverse events (AEs) it will not be recommenced without reference to the REC responsible for the study.

The outcome of the study (e.g., completed) will be reported to the REC responsible for the study within 90 days of completion of the last participant's final study procedures. In the event of the study being prematurely terminated a report will be submitted to the REC responsible for the study within 15 days.

A summary of the clinical study report will be submitted to the REC responsible for the study within 1 year of completion of the last participant's final study procedures.

The REC will be informed that Simbec-Orion is a commercial organisation and that the study is funded by Prokarium Ltd. The participants who take part in the clinical study will be paid for their inconvenience and have been informed that there will be no benefits gained by their participation. All potential conflicts of interest will be declared by the Investigators.

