10 INVESTIGATIONAL PLAN

10.1 Overall Study Design and Plan

This is a Phase I, randomised, double-blind, placebo-controlled, parallel group, single-centre study involving 45 healthy participants. The aim is to evaluate a combination vaccine against enteric fever comprising the live attenuated *Salmonella* strain ZH9 (previously tested in a number of clinical trials as a typhoid vaccine) and its modified derivative, ZH9PA, in which the typhoid antigens LPS O:9 and Flagellin H:d have been substituted by the Paratyphi A antigens, LPS O:2 and Flagellin H:a. ZH9PA has not previously been tested in humans; therefore, the first two cohorts comprise a dose escalation of this component alone, followed by a final cohort in which the combination is tested at a single dose level.

There will be 3 cohorts:

Cohort 1 will consist of 9 participants, who will receive 3 doses of 1×10^9 CFU of ZH9PA (6 participants) or placebo (3 participants).

Cohort 2 will consist of 18 participants, who will receive 3 doses of 1×10^{10} CFU of ZH9PA (12 participants) or placebo (6 participants).

Cohort 2 will not be initiated until all 9 participants of Cohort 1 have received 1 dose of ZH9PA or placebo, and the safety data, up to Day 7 are available. These safety data will be assessed by the safety review group, at which point the decision will be made as to whether proceeding with administration of the first dose of the higher dose level of ZH9PA (1×10^{10} CFU) to Cohort 2 is appropriate.

Cohort 3 will consist of 18 participants, who will receive 3 doses of 1×10^{10} CFU of ZH9PA and 1×10^{10} CFU of ZH9 (12 participants) or placebo (6 participants).

Cohort 3 will not be initiated until a minimum of 14 participants of Cohort 2 have received 1 dose of ZH9PA or placebo, and the safety data, up to Day 7 are available. These safety data will be assessed by the safety review group, at which point the decision will be made as to whether proceeding with administration of the first dose of the combination of ZH9PA and ZH9 to Cohort 3 is appropriate. In the event that fewer than 18 participants are dosed in Cohort 2, the remaining participants to complete the required number will be dosed with Cohort 3 or as a straggler group.

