Each cohort will start with a sentinel group that will consist of 2 participants, 1 will receive placebo and 1 will receive the relevant vaccine for that cohort. No further participants will be dosed until 24 hours after the second participant has received his/her dose. The rest of the cohort will be dosed provided there are no safety issues identified by the Investigator. This design allows maintenance of the “blind” until Day 70.

The clinical phase is anticipated to take place in Q4 2019 and Q2 2020. The end of the study is defined as last participant last visit.

The study will take place in the Clinical Pharmacology Unit of Simbec-Orion (Clinical Unit) under full medical and nursing supervision.

A schedule of all study assessments is provided in [Table 10.7.1](#).

Screening (Day -28 to Day -1)

Screening assessments will be performed from Day -28 to Day -1 to ensure the eligibility of participants. Assessments will be performed as per [Table 10.7.1](#).

Treatment Period (Day 0 to Day 84)

Participants will be admitted to the Clinical Unit on the morning of Day 0 with confirmation of eligibility and baseline assessments performed as per [Table 10.7.1](#). Following a 90 minute (min) fast prior to dose administration, participants will receive the first dose on Day 0, and then continue to fast for a further 90 mins post dose administration; water will be allowed. Following the completion of the 4h post-dose assessments and at the discretion of the Investigator, the participants will be discharged from the Clinical Unit. Participants will return to the Clinical Unit on Day 3 for safety assessments as per [Table 10.7.1](#). For the 7 days following the first dosing visit (Day 1 to Day 7) participants will be required to record their body temperature at home twice a day i.e. once in the morning and once in the evening (a thermometer and a diary will be provided to record body temperature). Participants will return to the Clinical Unit on Day 7 with the diary and to give a blood sample for the peripheral blood mononuclear cells (PBMC)/ALS assay; assessments will be performed as per [Table 10.7.1](#). Participants will return to the Clinical Unit on Day 14 for safety assessments; assessments will be performed as per [Table 10.7.1](#).

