10.2 Dose Escalation Procedures and Stopping Criteria

10.2.1 Dose Escalation Procedures

For each cohort, a summary of all relevant safety (AEs, laboratory safety tests, ECG, vital signs, subject recorded body temperature, concomitant medications) data (up to 7 days post-first dose) will be produced on behalf of the Principal Investigator. Planned doses may be modified following a review of emerging data. Progression to the next dose level and dose selection will be based on the available safety data from all participants for Cohort 1 prior to dosing Cohort 2 and a minimum of 14 participants¹ for Cohort 2 prior to dosing Cohort 3. Dose escalation will be dependent upon the accrual of acceptable safety data. If it is not appropriate to escalate the dose according to the proposed dose escalation schedule, then the same dose, an intermediate dose or a lower dose may be given following discussion between the Sponsor and the Principal Investigator (or deputy).

There will be a Telephone Conference at a pre-appointed time to involve the Simbec-Orion Project Manager and Principal Investigator (or deputy) and the Sponsor's representative(s), including the Sponsor's Responsible Physician. After discussion of all the data, the decision will be made whether to dose escalate and a written document (dose escalation approval form) signed by the Principal Investigator (or deputy) and Sponsor will be produced ratifying that decision. Full minutes, to be agreed by all parties, will be produced for each discussion regarding dose escalation and filed in the Investigator Site File (ISF). A copy of the signed dose escalation approval form will be provided to the Simbec-Orion Pharmacist and this will allow the IMP to be assembled for the next dose level.

Dose escalation stopping criteria are detailed in [Section 10.2.2.2](#).

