10.5.5 Removal of Participants from Therapy or Assessment

Each participant will be informed of his/her right to withdraw from the study at any time and for any reason.

An Investigator will withdraw a participant from the study at any time for any of the following reasons:

- If a participant experiences a serious or intolerable AE, that prevents him/her from continuing participation in the study.
- If a participant incurs a significant protocol violation which impacts on his/her safety or the scientific integrity of the study (this will be discussed on a case-by-case basis with the Sponsor).
- At the request of the Sponsor.
- If it is considered that the participant's health is compromised by remaining in the study or the participant is not sufficiently cooperative.
- If a participant is lost to follow-up.

Participants who meet one or more of the following stopping criteria will receive no further doses of the study vaccine but will be followed up for safety:

- Severe systemic reaction, e.g., anaphylaxis.
- Persistent febrile reaction ($\geq 38.5^{\circ}\text{C}$ for ≥ 12 hours) at the Investigator's discretion
- SAE related to the study agent (serious adverse reaction (SAR) or suspected unexpected serious adverse reaction (SUSAR))

The medical safety of the participant is of paramount importance when discussing study continuation.

The reasons for any participant withdrawal will be recorded on the study completion form of the electronic case report form (eCRF).

If a participant is withdrawn or chooses to withdraw from the study for any reason every possible effort will be made to perform the evaluations described for the post-study follow-up (see [Table 10.7.1](#)). The data collected from withdrawn participants will be included in the study report.

In the event of any abnormalities considered to be clinically significant, participants will be followed up with appropriate medical management until values are considered to be clinically acceptable. Referral or collaborative care will be organised if considered necessary.

A total of 45 participants are required to complete the study. Participants who withdraw from the study before receiving any IMP will be replaced. Participants who are withdrawn from the study due to significant drug-related AEs will not be replaced. Replacement of all other participants withdrawn from the study after receiving IMP will be decided on a case-by-case basis by the Principal Investigator (or deputy) and Sponsor.

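### The quantified criteria in 10.2.2.2 stop only dose escalation, so after the 24 h sentinel step no numeric rule holds dosing across a cohort, and in Cohort 3 there is no escalation left to stop

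*Combined protocol and SAP*

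**What the plan says.** Section 10.2.2.2 opens with "Dose escalation will be temporarily stopped pending evaluation of all available data if any of the following criteria are fulfilled". It then lists four triggers:

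1. A severe systemic related reaction in one sentinel or in more than 20% of a cohort.
2. A persistent related fever, with the same thresholds.
3. One related SAE.
4. Two participants in the same cohort with severe non-serious related reactions.

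Section 10.2.1 shows what escalation means: "Progression to the next dose level and dose selection will be based on the available safety data", using data up to 7 days after the first dose, from all of Cohort 1 and then from at least 14 participants of Cohort 2. Section 10.1 agrees: "Cohort 3 will not be initiated until a minimum of 14 participants of Cohort 2 have received 1 dose of ZH9PA or placebo". Section 10.6.4.2 places safety review meetings only between cohorts, and Cohort 3 is the last.

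Other provisions bear on continued dosing:

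- **Whole study (10.2.2.1):** "The study will be discontinued if any unacceptable safety findings are identified". No threshold is given. Section 6.1 adds "If the study is stopped due to adverse events (AEs) it will not be recommenced without reference to the REC responsible for the study".
- **Dose changes (10.2.1):** "Planned doses may be modified following a review of emerging data".
- **Sentinel step (10.1):** after 24 h, "The rest of the cohort will be dosed provided there are no safety issues identified by the Investigator".
- **Individual participant (10.5.5):** no further doses after a severe systemic reaction, a related SAE or, at the Investigator's discretion, a persistent fever. Withdrawal may also follow for other reasons, including "At the request of the Sponsor".
- **Each dosing visit (10.4.1, 10.4.2):** eligibility is re-confirmed, including the Investigator's view of suitability.

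**The concern.** ZH9PA is first in human and each participant is dosed three times, 21 days apart. The sponsor has already decided, in numbers, what would be worrying. Those numbers govern whether the next cohort opens. They do not govern whether participants already enrolled are dosed again.

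Suppose two Cohort 3 participants have severe related non-serious reactions in the week after the first dose. Criterion 4 is met, but the only action attached to it is to stop an escalation that does not exist. Whether the other 16 are re-dosed on Day 21 is then left to judgement. The same gap applies to second and third doses in Cohorts 1 and 2, because each escalation decision needs only Day 7 data after one dose.

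**Working it through.** **The plan's own figure.** The footnote to 10.2.1 says that 14 Cohort 2 participants guarantee at least 8 on active vaccine. With 6 on placebo, 14 − 6 = 8, so it reproduces.

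**What the criteria require.** More than 20% means at least 2 of 9 in Cohort 1 (22.2%) and at least 4 of 18 in Cohorts 2 and 3 (22.2%).

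**What each provision does after the sentinel step.**

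| Provision | Numeric trigger | Holds dosing in others in the cohort |
|---|---|---|
| 10.2.2.2 | Yes | No; stops escalation only |
| 10.2.2.1 | No | Yes, by discontinuing the study on judgement |
| 10.2.1 dose modification | No | Only if chosen |
| 10.5.5 stopping rules | Partly | No; affected participant only |
| Pre-dose eligibility checks | No | One participant at a time |

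No row combines a numeric trigger with a hold on the rest of the cohort. The stopping list in 10.5.5 matches criteria 1 to 3 in kind but does not include criterion 4.

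**How many doses are involved.** Inputs are the cohort sizes in 10.1 (active 6, 12, 12; total 9, 18, 18) and three doses each.

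- Active doses: (6 + 12 + 12) × 3 = 90. Second or third: (6 + 12 + 12) × 2 = 60.
- With placebo: 45 × 3 = 135, of which 45 × 2 = 90 are second or third doses.
- Data required for the two escalation decisions: 9 + 14 = 23 first doses (23/135 = 17%) and no later dose.
- Active doses in Cohort 3, all after the last escalation step: 12 × 3 = 36 of 90. This is a minimum. Any Cohort 1 or 2 dose still due when Cohort 3 opens adds to it, and the total depends on a calendar that the protocol does not fix.

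**What a dosing pause would cost in false alarms.** The protocol gives no expected rate of severe related reactions, so I assume a true rate p of 2% to 5% per participant, with independence. For criterion 4 in a cohort with n contributing participants, P(X ≥ 2) = 1 − (1 − p)^n − np(1 − p)^(n−1).

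| Contributing participants | p | Cohort 1 | Cohort 2 | Cohort 3 | At least one cohort |
|---|---|---|---|---|---|
| Active only (6, 12, 12) | 2% | 0.006 | 0.023 | 0.023 | 1 − 0.9943 × 0.9769² = 0.051 |
| Active only (6, 12, 12) | 5% | 0.033 | 0.118 | 0.118 | 1 − 0.9672 × 0.8816² = 0.248 |
| All (9, 18, 18) | 2% | 0.013 | 0.050 | 0.050 | 1 − 0.9869 × 0.9505² = 0.108 |
| All (9, 18, 18) | 5% | 0.071 | 0.226 | 0.226 | 1 − 0.9288 × 0.7735² = 0.444 |

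The lower pair of rows supposes that placebo events are judged related at the same rate. That is possible because relatedness is assessed blind.

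**The case against.** The strongest reply is that re-dosing is far from unguarded. The sentinel hold is written and applies in every cohort, so a sentinel reaction seen within about 24 h does hold the remaining first doses. Section 10.5.5 stops further doses in a participant with a severe systemic reaction or a related SAE. Section 10.2.2.1 is mandatory once findings are judged unacceptable. Section 10.2.1 calls for a Day 7 safety summary for each cohort, which on its face includes Cohort 3. Participants needing antibiotics for an infection between Day 0 and Day 49 get no further doses (10.6.10), adverse events of special interest reach the Sponsor's physician within 24 h (10.7.1.3.1), and urgent safety changes can take effect at once (11.2).

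All of that stands, and it limits the point. A reader might infer that nothing would stop dosing after a related SAE, or that the sponsor means to carry on. The documents do not support either. The affected participant's doses stop by rule, and the criteria name the ZH9PA/ZH9 vaccine although ZH9 is given only in Cohort 3. Coverage of that cohort was therefore probably intended and the opening sentence is imprecise.

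The reply does not supply a numeric hold at cohort level. The sentinel hold rests on Investigator judgement and covers first doses only. The Day 7 summary has no decision attached to it in Cohort 3. The remaining safeguards are individual or unquantified.

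**Conclusion.** The point holds in this form: after the 24 h sentinel step, no quantified criterion triggers a cohort-level hold on dosing, and once Cohort 3 has started the criteria in 10.2.2.2 have no escalation to stop. The dose counts rest only on the planned cohort sizes and three doses each. The pause probabilities rest on the assumed 2% to 5% rates and on independence, and cover criterion 4 alone.

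This is a gap between thresholds the sponsor has already set and the action they trigger. It is not evidence that participants are unprotected. In a first-in-human trial it should be closed, because two thirds of the active doses (60 of 90) lie where the numeric rules do not reach.

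**What to change.** Replace the opening sentence of 10.2.2.2 with wording such as:

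*If any criterion below is met in any cohort, including Cohort 3, all further dosing (first, second and third doses) in all cohorts, and any dose escalation, is temporarily suspended while all available data are evaluated. Dosing in each cohort resumes only after a decision documented and signed by the Principal Investigator (or deputy) and the Sponsor.*

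The four criteria stay as they are. Suspending all cohorts avoids arguing over whether a reaction to the combination should pause Cohort 2, which receives the same ZH9PA dose; the signed decision can then release cohorts one at a time.

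A delayed-dose rule follows from this, because doses are 21 days apart and Table 10.7.1 allows no window on Days 21 and 42. State a maximum delay (for the sponsor to set), time later visits from the actual dose, and omit a dose beyond the limit while continuing safety follow-up.

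Costs:

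- **Unnecessary pauses:** 5% to 25%, or 11% to 44% with placebo events counted, for criterion 4 in at least one cohort under the assumed rates. The other criteria would add to this.
- **Immunogenicity sampling:** shifted for paused participants.
- **Blinding:** the review should stay blinded where possible, since 10.6.9 withdraws any participant whose code is broken.
- **Approval:** probably a substantial amendment under 11.2, needing REC and MHRA approval.

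No dose, cohort size or threshold changes.

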10.3 Discussion of Study Design, including the Choice of Control Groups

This is a Phase I, first in human, randomised, double-blind, placebo-controlled, parallel group, study. Randomised, double-blind studies are the gold standard methodology to assess the safety, tolerability and efficacy of products and therefore, this design has been used for this study. In the case of this study, it will remain fully blinded until Day 70, when a stool sample is taken to assess if participants are shedding the bacterial strains of the vaccine in their faeces. The Investigators and the Monitor will be unblinded to the treatment allocation of participants who have a positive result for *Salmonella* and the participant will receive a course of antibiotics.

No benefit to participants is expected, as efficacy has not been evaluated for the ZH9/ZH9PA combination or for ZH9PA on its own; therefore, use of placebo as the control is considered acceptable in the healthy participants participating in the study. The use of the placebo control allows an assessment of the immune response and provides a background incidence of adverse events.

Previous work with ZH9 has shown that the double mutation does appropriately attenuate the bacteria, however it is known that the bacterial strains that make up the vaccine can be shed in the stools of participants. The vaccine strains are genetically modified organisms, and as such it is necessary to reduce environmental exposure and stool cultures are taken to ensure that participants are not shedding.

There remains a theoretical risk of the vaccine strains causing a systemic infection and so body temperatures will be taken for 7 days post each dose of vaccine. The vaccine strains are

sensitive to several antibiotics, which can be used to treat an infection in the unlikely event such an event occurs.

Three doses are to be studied, as vaccines usually require more than one dose to induce a robust immune response.

10.4 Selection of Study Population

45 participants will be required to complete the study.

The study is to be conducted in healthy participants, which will be the ultimate target population for a vaccine. While it is anticipated an immune response will be induced in participants receiving the vaccine candidate, it is not known whether the immune response is protective and; therefore, participants are not expected to derive any therapeutic benefit from taking part in the study. A healthy participant population with carefully considered inclusion / exclusion criteria will avoid the potential for interaction of ZH9PA/ZH9 with any underlying disease state or concomitant medication that it may be necessary for patients to take, while ensuring that participants are fit and well enough for participation in the study.

ZH9PA has not been previously administered to humans; therefore, its effects in humans are as yet unknown.

The following eligibility criteria are designed to select participants for whom protocol treatment and procedures are considered appropriate. All relevant medical conditions should be taken into consideration when deciding whether this protocol is suitable for a particular participant.

